5.3.2 Exclusion Criteria

5.3.2.1 Phase Ia/Ib Parts

Subjects are not eligible for the Phase Ia or Ib parts of the trial if they fulfill any of the following exclusion criteria:

1. Prior treatment consisting of:
 - a. Chemotherapy, immunotherapy, hormonal therapy, biologic therapy, or any other anticancer therapy or IMP within 28 days of first trial drug intake (6 weeks for nitrosoureas or mitomycin C) for Phase Ia, Arm A subjects, and any prior therapy for Phase Ib subjects. For subjects with rapidly growing tumors localized in the head and neck region or thorax where the treating physician cannot wait for 28 days, inclusion may take place if there is no residual toxicity from previous treatment (maximum Common Terminology Criteria for Adverse Events [CTCAE] Grade 1)
 - b. Prior RT to the same region within 12 months (Phase Ia, Arm A; subjects with tumors localized in the head and neck region or thorax) or at any time previously (Phase Ia, Arm B; treatment-naïve subjects with SCCHN and Phase Ib; treatment-naïve subjects with Stage III A/B NSCLC or SCCHN)
 - c. Extensive prior RT on $\geq 30\%$ of bone marrow reserve as judged by the Investigator or prior bone marrow/stem cell transplantation within 5 years before trial start
2. Residual toxicity due to prior therapy with no return to baseline or \leq Grade 1 (except alopecia according to CTCAE v4.03)
3. Surgical intervention, including biopsies and dental root surgeries, within 28 days prior to the first dose of IMP administration or having participated in an interventional clinical trial within 28 days prior to the first dose of IMP administration for Phase Ia/Ib. **Needle biopsies are not considered as surgery.**
4. Poor vital organ functions defined as:
 - a. Bone marrow impairment as evidenced by hemoglobin <10.0 g/dL (5.7 μ mol/L), neutrophil count $<1.0 \times 10^9$ /L, platelets $<100 \times 10^9$ /L
 - b. Renal impairment as evidenced by serum creatinine $>1.5 \times$ upper limit of normal (ULN)
 - c. Liver function abnormality as defined by total bilirubin $>1.5 \times$ ULN or aspartate aminotransferase (AST)/alanine aminotransferase (ALT) $>2.5 \times$ ULN (except for subjects with liver involvement, who can have AST/ALT $>5 \times$ ULN)
5. Significant cardiac conduction abnormalities, including a history of long QTc syndrome and/or pacemaker, or impaired cardiovascular function such as New York Heart Association classification score > 2

6. Hypertension uncontrolled by medication

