M3814 will be provided as tablet formulation of 50 mg for oral administration. Dosing schedule of the tablet formulation follows the description given for the capsule formulation above. The tablet formulation will be initially assessed in Phase Ia Arm A taking into account the available safety, tolerability and PK results from the capsule. Standard 3+3 dose escalation design criteria will apply. Comparison of single dose PK data between the tablet and the capsule will guide to define the tablet doses in Phase Ia Arm B and in the Phase Ib parts.

For subjects in Arm B receiving cisplatin:

- There will be no dose escalation of cisplatin above the protocol-specified dose. However, cisplatin dose re-escalation after an initial dose reduction, following the manufacturer's label, is permitted.
- Dose modifications for toxicity should be independently assessed prior to dose administration at each visit following institutional guidelines or [Table 13](#) in the absence of such guidelines.
- Prophylactic granulocyte-colony stimulating factor (G-CSF) may be implemented if neutropenia results in dose reduction or dose delay at prior doses, as suggested in the ASCO guidelines. Therapeutic use of hematopoietic colony-stimulating factors is permitted following ASCO guidelines.
- In the event a subject experiences neutropenia, and G-CSF is initiated, and neutropenia recovers within 48 hours after beginning treatment with G-CSF, G-CSF may be implemented in the management of neutropenia in this subject to avoid dose reductions or holding a dose.

Hemoglobin must be ≥ 10 g/dL at FD 1 and must be ≥ 9 g/dL for all subsequent doses. If hemoglobin is <9 g/dL then appropriate measures according to standard clinical practice must be taken prior to any further dose administration.

Table 13

Dose Modifications for M3814, Radiotherapy, and Cisplatin During the Trial

Toxicity	Dose Modifications		
	M3814 ^a	Radiotherapy ^b	Cisplatin (only for Arm B and in the absence of institutional guidance on cisplatin dose modifications)
Toxicities in Radiation Field Grade 4 
 Mucositis (mucosal inflammation) Radiation dermatitis 	Temporarily interrupt treatment. Resume treatment once severity resolves to Grade \leq 3.	Temporarily interrupt treatment. Resume treatment once severity resolves to Grade \leq 3.	Temporarily interrupt treatment. Resume treatment once severity resolves to Grade \leq 3.

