Systemic Toxicities 
 Febrile neutropenia Grade 3 thrombocytopenia with medically concerning bleeding Hematologic Toxicities: Any Grade \geq 4 toxicity, excluding: 
 Grade 4 neutropenia lasting for \leq 5 days and not associated with fever Isolated Grade 4 lymphocytopenia without clinical correlate 	Temporarily interrupt treatment. Resume treatment (at the same dose) once severity resolves to Grade \leq 1 or Baseline. In case of a second recurrence at the same grade, permanently discontinue IMP.	No action to be taken.	Febrile neutropenia and Grade 3 thrombocytopenia with bleeding: permanent 25% dose reduction. If on the day of scheduled treatment with cisplatin ANC is $<$ 1500/mm 3 , hold treatment until ANC \geq 1500/mm 3 , then treat at 100% dose. If on the day of scheduled treatment with cisplatin the platelet count is $<$ 75,000/mm 3 , hold treatment until platelets are $>$ 75,000/mm 3 , then treat at 100% dose.
Systemic Toxicities 
 Nonhematologic Toxicities 
 Any Grade \geq 3 toxicity, excluding: 
 Diarrhea of Grade \geq 3 (\leq 3 days duration) following adequate and optimal therapy Nausea and vomiting of Grade \geq 3 (\leq 3 days duration) with adequate and optimal therapy Fatigue or headache of Grade 3 (\leq 7 days duration) following initiation of adequate supportive care Any other single laboratory values of Grade \geq 3 out of the normal range that have no clinical significance, and that resolve to Grade \leq 2 with adequate measures within 7 days 	Temporarily interrupt treatment. Resume treatment (at the same dose) once severity resolves to Grade \leq 1 or Baseline. In case of a second recurrence at the same grade, permanently discontinue IMP. In case of Grade \geq 3 liver enzyme values, the subject must be monitored at least every 4 days until recovery to Grade \leq 2.	No action to be taken.	Institutional guidelines.

- Evidence of study treatment-related hepatocellular injury for more than 3 days, such as > 5-fold elevations above the ULN of ALT or AST (CTCAE Grade 3 or 4) with or without elevation of serum total bilirubin to > 2 x ULN, without initial findings of cholestasis (elevated serum a kaline phosphatase) or other apparent clinical causality.

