6.3.1.1.1 Predosing Considerations for Cisplatin

Cisplatin is administered to SCCHN subjects as part of the trial. As with most cytotoxic regimens, this drug is preceded and accompanied by supportive care. General guidance on the use of cisplatin is provided. However, Investigators are referred to and need to follow the package insert, the summary of product characteristics (SmPC), and their local policies/instructions for the administration of cisplatin.

Main predosing measures for cisplatin are provided in Table 14 below and need to be assessed for the individual subject prior to the first, but also for subsequent administrations of cisplatin. Note that some measures may begin several days before actual treatment.

Table 14 Predosing Considerations for Cisplatin

Issue/Indication	Recommended Steps
Pre-emesis	Follow current MASCC/ESMO ^a or NCCN ^b guidelines for chemotherapy-induced nausea and vomiting for a “high risk” regimen
Hydration/nephrotoxicity	Per package insert/SmPC for cisplatin ^c . Cisplatin causes severe cumulative nephrotoxicity. A urine output of 100 mL/hour or greater will tend to minimize cisplatin nephrotoxicity. Adequate hydration must therefore be maintained to cause sufficient diuresis prior to, during and after treatment with cisplatin. Next to iv infusion, forced diuresis may be required and moreover subjects are to be requested to drink appropriate quantities of liquids for 24 hours after cisplatin infusion to ensure adequate urine secretion.

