Myelosuppression/neutropenia	Refer to the current package insert/SmPC and local guidance for modifications in dose and schedule of cisplatin ^c . Cisplatin dose should be withheld if platelet count is less than 75,000 cells/mm ³ or neutrophil count is less than 1500 cells/mm ³ . Primary prophylaxis with G-CSF in order to reduce the risk of febrile neutropenia (FN) is not recommended, according to ASCO ^d and ESMO guidelines. FN is defined as oral temperature >38.5°C or two consecutive readings of >38°C for 2 hours and an absolute neutrophil count <0.5 × 10 ⁹ /L, or expected to fall below 0.5 × 10 ⁹ /L. Secondary prophylaxis with CSFs is recommended for subjects who experienced a neutropenic complication from a previous cycle of chemotherapy (for which primary prophylaxis was not received), in which a reduced dose or treatment delay may compromise disease-free or OS or treatment outcome. The secondary prophylaxis should follow ASCO or ESMO or local guidelines. The dosage instructions should follow the local guidelines or the ASCO or ESMO guidelines.
Ototoxicity/neurotoxicity	Per package insert/SmPC for cisplatin ^c . Cisplatin is proven to be cumulative ototoxic and neurotoxic. Neurologic examination and monitoring of potential ototoxicity is to be performed prior to each cisplatin dosing and during the treatment.

ASCO = American Society of Clinical Oncology; CSF = colony stimulating factor; ESMO = European Society for Medical Oncology; FN = febrile neutropenia; G-CSF = granulocyte-colony stimulating factor; iv = intravenous; MASCC = Multinational Association of Supportive Care in Cancer; NCCN = National Comprehensive Cancer Network; SmPC = summary of product characteristics; OS = overall survival.

^aAnnals of Oncology 21 (Supplement 5): v232–v243, 2010

^bNCCN Guidelines Antiemesis version 2/2016

^c<https://www.medicines.org.uk/emc/medicine/25944> (Last Updated on eMC 09 January 2015)

^dJ Clin Oncol 33:3199-3212

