7.1.2 Treatment Period

7.1.2.1 Phase Ia Part: Arm A and Arm B (Fraction Days 1 to 10)

Eligible subjects will receive M3814 during the period in which RT is given.

The following assessments will be performed on Fraction Days 1, 6 and 10; if Fraction Day 10 is on a Friday, PK, CC1 safety laboratory, and urinalysis sampling must be done on Fraction Day 9:

- Review of inclusion and exclusion criteria (Fraction Day 1 only)
- Assessment of vital signs (blood pressure, heart rate, and body temperature), body weight (see Section 7.4.4 for details)

- Physical examination
- Clinical examination of bleeding (including petechiae, in skin, in the sclera of the eye, oral mucosa)
- Evaluation of all tissues in the RT area (Fraction Day 6 and 10 only)
- ECOG PS (Fraction Day 10 only)
- Assessment of AEs
- Documentation of concomitant medications
- Safety laboratory (hematology, serum chemistry and coagulation)
- Urinalysis (Fraction Day 10 only)
- 12-lead ECG including QTcF (Fraction Day 1 and 10)
- Collection of PK blood samples
- Availability of archival tumor material, either as a block or slides. If no archival material is available then a fresh biopsy should be taken

CCI

The following assessments will be performed on Fraction Day 2:

- Collection of PK blood samples (predose)

CCI

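### Arm B's numeric entry limit for neutrophils (1.0 x 10^9/L) lies below the count at which the protocol's own guidance withholds cisplatin (1.5 x 10^9/L)

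*Protocol*

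**What the plan says.** **Entry.** Exclusion 4a (Protocol 5.3.2.1) begins "Bone marrow impairment as evidenced by hemoglobin" and goes on to list three counts. A subject is excluded for hemoglobin below 10.0 g/dL, neutrophils below 1.0 x 10^9/L or platelets below 100 x 10^9/L. The item covers all of Phase Ia/Ib and has no separate Arm B value. PDEV12 in SAP Appendix 1 repeats 1.0.

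**Cisplatin.** Table 13 (Protocol 6.3.1) reads "If on the day of scheduled treatment with cisplatin ANC is" below 1500/mm3, and then holds the infusion until recovery, "then treat at 100% dose". Its cisplatin column applies only to Arm B and only "in the absence of institutional guidance on cisplatin dose modifications". Table 14 (6.3.1.1.1) lists, under recommended steps, withholding cisplatin if the "neutrophil count is less than 1500" cells/mm3. The text introducing Table 14 says its measures "need to be assessed for the individual subject prior to the first, but also for subsequent administrations of cisplatin".

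**Start of treatment.** The one blood count with an explicit FD1 floor in 6.3.1 is hemoglobin, which must be at least "10 g/dL at FD 1 and must be" at least 9 g/dL afterwards. Protocol 7.1.2 schedules "Review of inclusion and exclusion criteria (Fraction Day 1 only"). Section 5.4 starts M3814 once eligibility is met. Section 6.3.1 permits a cisplatin delay of up to one week.

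**Evaluability.** The DLT period runs from the first M3814 dose (7.4.1.5, 8.3.1). The DE set requires 80% of planned M3814 and RT and completion of the DLT period, or a DLT. It sets no minimum for cisplatin (Protocol 8.4; SAP 8.2).

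**The concern.** Phase Ia Arm B is meant to find the M3814 dose that is tolerable with cisplatin chemoradiation. The numeric entry criterion is shared with Arm A, which receives no cisplatin, and it admits subjects whose first infusion the protocol's own guidance would postpone. M3814 and RT need not wait for cisplatin. Such a subject would spend the first part of the DLT period on M3814 plus RT alone, and would still be counted as evidence on the triple combination.

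There are two things at stake. One is interpretability: cohorts have 3 subjects, so one such subject is a third of the new evidence for a dose decision. The other is safety: a subject who starts with a low neutrophil count has less marrow reserve when cisplatin is added.

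**Working it through.** The plan has no figure of its own to reproduce here. The check is a comparison of limits in common units, followed by a trace of what the rules allow.

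**1. Units.** 1500/mm3 = 1500 x 10^6/L = 1.5 x 10^9/L.

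**2. Limits side by side (Arm B).**

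| Count | Lowest value admitted by 4a | Cisplatin withheld below (Tables 13 and 14) | Explicit FD1 floor in 6.3.1 |
|---|---|---|---|
| Neutrophils, x 10^9/L | 1.0 | 1.5 | none |
| Platelets, x 10^9/L | 100 | 75 | none |
| Hemoglobin, g/dL | 10.0 | none stated | 10 |

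Platelets leave a margin of 100 - 75 = 25 x 10^9/L above the withholding limit. For hemoglobin, the entry limit and the FD1 floor agree. For neutrophils the order is reversed, with a shortfall of 1.5 - 1.0 = 0.5 x 10^9/L.

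**3. Trace of an Arm B subject at 1.2 x 10^9/L.**
- Exclusion 4a is not met, since 1.2 is above 1.0. The FD1 review in 7.1.2 applies the same limit.
- Inclusion 1a asks for eligibility for concurrent cisplatin. It gives no count, so the investigator decides.
- If the subject is judged eligible, 5.4 lets M3814 start.
- Table 14 advises withholding the first infusion. Table 13 says the same where the site has no rule of its own.
- The hematologic row of Table 13 interrupts M3814 only for febrile neutropenia, Grade 3 thrombocytopenia with bleeding, or non-exempt Grade 4 or worse toxicity. It takes no action on RT.
- The DLT clock starts with M3814. The subject can enter the DE set whatever cisplatin is given.

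**4. Size of a delay.** With the one-week delay allowed in 6.3.1, 12 - 1 = 11 weeks of the DLT window still follow the first infusion. On the 100 mg/m2 schedule, Table 13 postpones the dose and then gives it in full, so the planned total remains 2 x 100 = 200 mg/m2.

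**5. How many subjects.** The documents give no distribution of entry counts. The 0-5% range is an assumption:
- Phase Ia Arm B: 0.05 x 30 = 1.5, so 0-1.5 subjects.
- Phase Ib Arm B: 0.05 x 27 = 1.35, so 0-1.4 subjects.
- Both: 0.05 x 57 = 2.85, so 0-2.9 subjects.

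Phase Ib Arm B has the same entry gap but no DLT period.

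**6. Would the report show it?** The summaries in SAP section 13 give number of infusions, cumulative dose and relative dose intensity. A dose given late but in full leaves all three unchanged. The delay would appear only in listings with administration dates (SAP 13) or the date of first cisplatin (SAP 10.1).

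**The case against.** The strongest reply is that 1.5 x 10^9/L is not a binding trial-wide rule. The Table 13 cisplatin column gives way to institutional guidance, and Table 14 is a set of recommended steps beside the label and local policy. A site with a lower threshold would have a smaller gap or none. Inclusion 1a is also a real second filter. It is reviewed again on FD1, and an investigator who may not give cisplatin that day has written grounds to retest or not to start. Low counts should be rare in treatment-naive subjects, and the Safety Monitoring Committee (SMC) reviews all available safety data. All of this stands, and it is why the point is a small one. It does not close the gap: the only number in the criteria is 1.0, and sites may apply inclusion 1a differently.

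A reader might infer more from the mismatch. The documents do not support these stronger readings:
- **That the protocol contradicts itself.** It does not. A subject can be eligible while one component is briefly delayed, and 6.3.1 provides for that.
- **That the DLT rate is biased low, so the MTD is set too high.** Lower early cisplatin exposure points one way and lower marrow reserve the other. Uncomplicated Grade 4 neutropenia of up to 5 days is not a DLT in any case. The net direction cannot be determined.
- **That cisplatin dose is lost.** On the two-dose schedule, Table 13 gives the dose in full. For the weekly schedule the protocol does not fix the number of infusions, so no loss can be calculated.
- **That counts go unchecked before infusions.** Sections 6.3.1 and 6.3.1.1.1 require assessment before each dose.

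**Conclusion.** The concern holds as a minor misalignment. Exclusion 4a lets an Arm B subject with neutrophils of 1.0 to 1.49 x 10^9/L meet the numeric criteria, although the protocol's cisplatin guidance would withhold the first infusion at that count. Such a subject can start M3814, RT and the DLT period with cisplatin delayed, and can count in the DE set.

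The effect is small. It requires that the site follows Table 14, or Table 13 for want of its own rule, and that the investigator still judges the subject eligible for cisplatin under inclusion 1a. Its direction is unknown and its frequency is not in the documents; the 0-5% range is assumed only to show scale. No harm to the primary endpoint is demonstrated. The case for change is that aligning the two limits makes the Arm B DLT data easier to interpret, helps safety and costs little.

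**What to change.** In exclusion 4a, for Arm B only, set the screening neutrophil limit to <1.5 x 10^9/L. Keep 1.0 for Arm A. The retest within the screening period that 5.3.2.1 already allows would apply. Update PDEV12 in the Phase Ia SAP. Phase Ib has a separate analysis plan (SAP section 4), so change the matching item there too.

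Word it as a screening limit. A rule holding M3814 and RT on FD1 until neutrophils recover is not recommended, because it could delay curatively intended RT, which the present design lets proceed. A fall after screening would be left to the existing cisplatin rules.

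The cost is amendment wording for one exclusion item and one deviation item in each of the two plans. An occasional Arm B subject would be retested or excluded. No visit or scheduled sample is added.

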6.3.1.1 Dosage and Administration of Concurrent Cisplatin

The currently proposed regimen for treatment-naïve subjects with SCCHN in Phase Ia (Arm B) and Phase Ib (SCCHN expansion cohort) consists of QD administration of M3814 on each RT fraction day together with the SoC (cisplatin).

On Fraction Days 1 and 31 for the 100 mg/m² dose, or weekly for the 40 mg/m² dose, cisplatin will be given according to institutional guidelines.

The timing of radiotherapy after the administration of cisplatin will also follow institutional guidelines, applicable for Phase Ia, Arm B (dose escalation) and the Arm B (SCCHN) expansion cohort only. Administration of M3814 will take place 1.5 hours (\pm 30 minutes) before the start of radiotherapy (see Section 6.3.1).

Body surface area (BSA) should be calculated based on a standard formula, such as the Mosteller formula [9]:

$$\text{BSA (m}^2\text{)} = ([\text{Height(cm)} \times \text{Weight(kg)}]/3600)^{\frac{1}{2}} \quad \text{e.g. BSA = square root}([\text{cm} \times \text{kg}]/3600)$$

or, in inches and pounds:

$$\text{BSA (m}^2\text{)} = ([\text{Height(in)} \times \text{Weight(lbs)}]/3131)^{\frac{1}{2}}$$

If there is a change in body weight of at least 10 percent, the individual cisplatin dose should be recalculated. Otherwise, the initial BSA should be utilized for subsequent doses.

6.3.1.1.1 Predosing Considerations for Cisplatin

Cisplatin is administered to SCCHN subjects as part of the trial. As with most cytotoxic regimens, this drug is preceded and accompanied by supportive care. General guidance on the use of cisplatin is provided. However, Investigators are referred to and need to follow the package insert, the summary of product characteristics (SmPC), and their local policies/instructions for the administration of cisplatin.

Main predosing measures for cisplatin are provided in Table 14 below and need to be assessed for the individual subject prior to the first, but also for subsequent administrations of cisplatin. Note that some measures may begin several days before actual treatment.

Table 14 Predosing Considerations for Cisplatin

Issue/Indication	Recommended Steps
Pre-emesis	Follow current MASCC/ESMO ^a or NCCN ^b guidelines for chemotherapy-induced nausea and vomiting for a “high risk” regimen
Hydration/nephrotoxicity	Per package insert/SmPC for cisplatin ^c . Cisplatin causes severe cumulative nephrotoxicity. A urine output of 100 mL/hour or greater will tend to minimize cisplatin nephrotoxicity. Adequate hydration must therefore be maintained to cause sufficient diuresis prior to, during and after treatment with cisplatin. Next to iv infusion, forced diuresis may be required and moreover subjects are to be requested to drink appropriate quantities of liquids for 24 hours after cisplatin infusion to ensure adequate urine secretion.
Myelosuppression/neutropenia	Refer to the current package insert/SmPC and local guidance for modifications in dose and schedule of cisplatin ^c . Cisplatin dose should be withheld if platelet count is less than 75,000 cells/mm ³ or neutrophil count is less than 1500 cells/mm ³ . Primary prophylaxis with G-CSF in order to reduce the risk of febrile neutropenia (FN) is not recommended, according to ASCO ^d and ESMO guidelines. FN is defined as oral temperature >38.5°C or two consecutive readings of >38°C for 2 hours and an absolute neutrophil count <0.5 × 10 ⁹ /L, or expected to fall below 0.5 × 10 ⁹ /L. Secondary prophylaxis with CSFs is recommended for subjects who experienced a neutropenic complication from a previous cycle of chemotherapy (for which primary prophylaxis was not received), in which a reduced dose or treatment delay may compromise disease-free or OS or treatment outcome. The secondary prophylaxis should follow ASCO or ESMO or local guidelines. The dosage instructions should follow the local guidelines or the ASCO or ESMO guidelines.
Ototoxicity/neurotoxicity	Per package insert/SmPC for cisplatin ^c . Cisplatin is proven to be cumulative ototoxic and neurotoxic. Neurologic examination and monitoring of potential ototoxicity is to be performed prior to each cisplatin dosing and during the treatment.

ASCO = American Society of Clinical Oncology; CSF = colony stimulating factor; ESMO = European Society for Medical Oncology; FN = febrile neutropenia; G-CSF = granulocyte-colony stimulating factor; iv = intravenous; MASCC = Multinational Association of Supportive Care in Cancer; NCCN = National Comprehensive Cancer Network; SmPC = summary of product characteristics; OS = overall survival.

^aAnnals of Oncology 21 (Supplement 5): v232–v243, 2010

^bNCCN Guidelines Antiemesis version 2/2016

^c<https://www.medicines.org.uk/emc/medicine/25944> (Last Updated on eMC 09 January 2015)

^dJ Clin Oncol 33:3199-3212

